Randomized studies in drug-resistant epilepsy typically involve addition of new anti-epileptic drugs. However, in clinical practice, if the patient is already taking multiple drugs, then substitution of one of the current medications commonly occurs, despite little evidence supporting this approach.²² The choice of the substitution drug depends on the mechanism of action, the pharmacokinetic profile, drug-drug interaction, and the risk of seizure exacerbation as well as patients-related factors. The new combination is intended to maximize efficacy and minimize toxicity. However, the availability and cost-effectiveness should also be

taken into consideration since the patient would not reach the goal of ideal combination of drugs if they could not afford it nor even get the medication. ²³⁻²⁶ Another considerable case is one of drug resistance patterns in which at the first-time patients may not responsive to treatment yet they change into a state that is responsive to the medication. ²⁷ The choice of substitution therapy may originate from firs-line AEDs since evidences have shown they have equal efficacy to those of second-line ones. However, there is still lack of evidence whether the drug resistance pattern occur if the substitution drug is originated from first-line AED even more if it has ever been given prior to the current drug combination. ²⁷ The study aims to analyzed the efficacy and safety of first-line AEDs as substitution therapy in drug-resistant epilepsy children.

Primary Objective

The primary outcome of the research is to analyze the proportion of responders, who are defined as subjects who get 50% of seizure reduction.

Secondary Objectives

There are some secondary objectives of the study. The first one is to analyze the differences of improvement of quality of life, EEG feature and time to achieve seizure reduction, between the intervention and the control group. Besides, the research will describe the clinical characteristics, adverse effects of the drugs and laboratory features related to the adverse effects, among children with drug-resistant epilepsy. Furthermore, it will explain factors influencing the reduction of seizure frequency

Study Design

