This protocol is intended for a multicenter open label experimental, randomized controlled trial on the efficacy and safety of using first line AEDs as substitution therapy in childhood drug-resistant epilepsy. It will prospectively follow 100 children up during 14 weeks that consist of baseline, intervention, and post-intervention phases. While the intervention consists of 6 steps, as described at the Figure 1 below.

[figure not shown]

Figure 1. Timeline of the intervention phases

The study will be conducted at pediatric outpatient clinic of 3 referral hospitals in Jakarta, Cipto Mangunkusumo Hospital, Harapan Kita Hospital and Fatmawati Hospital. Children who are diagnosed with drug-resistant epilepsy receiving levetiracetam or topiramate will be enrolled in the study. Enrollment begins as soon as the research ethics committee approval is obtained from The Ethics Committee of The Faculty of Medicine, University of Indonesia-Cipto Mangunkusumo Hospital. The study will be closed after the last recruited patient has been followed up for the required 14 weeks.

All recruited children will be examined for monitoring at the hospital where the intervention is initiated. To avoid selection bias, all patients who met the inclusion criteria are divided into two groups, the intervention and control groups. Prospective participants and their parents will be provided with information related to the study. Patients will then fill out an information sheet containing demographic data, comorbidities, developmental history, school history, history of drug consumption, as well as history of seizures and patient complaints. All the data will be extracted and recorded on the case report form. Patients and their parents should be informed that participation is voluntary and they are free to withdraw from the study at any time. They should also be informed that refusal to participate or withdraw from the study will not affect the quality of treatment received. In the event of their withdrawal, it will be explained that the data collected so far is irrevocable, and we will seek consent to use such data in the final analysis if necessary.

Study procedure

Study procedures are depicted in Figure 2. The patients who are eligible for the study and have given their consents, will be enrolled, divided into 2 groups, the intervention and control, then start the 3-day baseline phase. In this phase, data such as demographic, clinical characteristic

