including seizure frequency, seizure type, seizure onset, medication history, family history of seizure, and also developmental stages, will be recorded from electronic medical record. Besides, the CT-scan or MRI are also collected from the same source. After that, their quality of life will be assessed by QOLCE-55 validated questionnaire through self-guided report. Furthermore, the laboratory investigation and EEG will be performed.

The next phase is intervention phase, started from initial step and ended by the maintenance of new combination therapy, which takes with overall 12 weeks. Initially, the substitution drugs with each initial dose are consumed. The drugs consist of valproic acid for the generalized and carbamazepine for focal epilepsies. On the other hand, the control group will take lamotrigine or clobazam for generalized and oxcarbazepine for focal ones. The phase continuous to titration dose, in which, the dose is raised gradually until it causes 50% of seizure reduction, and the next step is maintained the dose for about 2 weeks.

The following is tapering-off and after that stopping the substituted drug, levetiracetam or topiramate, which is determined by considering individual condition. Yet, if the seizures increase more than one and a half time of the previous frequency during the phases, the intervention will be ended immediately. On the contrary, if the condition is better, then the children go to the maintenance of new combination, that is the substitution drug and the old drugs in which the seizures do not go up or even better keep going down. The children who complete all of the phases are categorized as responder. In case if the intervention is ended, the subjects will be given the former combination therapy with adjusted doses in order to decrease the seizures until reaching the pre-intervention condition. The subjects are categorized as non-responder, and will be dropped-out. The other criteria of drop-out are resignation, non-compliance of study procedure, and death in term of other causal not related to the study. While in term of lost to follow-up, is intended for those who do not attend the study without any possible reasons.

[figure not shown]

Figure 2. flow-chart of the study

Maintenance the dose of the new combination therapy that consist of the new drug and

Maintenance

old drug after stopping the substituted drug

Inclusion criteria

- 1. Children age at 1 18 years old

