- 2. Children diagnosed as drug-resistant epilepsy by pediatric neurologists, diagnosis was based on the ILAE 2017 criteria
- 3. Children will have got at least 3 months of combination therapy that consists of levetiracetam of topiramate with optimal of therapeutic dosages

Exclusion criteria

- 1. Non-convulsive epilepsy
- 2. Suffered from status epilepticus in the prior 3 months before the study begins
- 3. Past medical history of idiosyncrasies or severe adverse drug reactions caused by the substitution therapy that will be given

Instrument of the study

QOLCE-55 questionnaire

Once the children are enrolled, quality of life will be assessed by using validated QOLCE-55 questionnaire. It is parent-reported and self-administered questionnaire which assess quality of life children with epilepsy age 4-18 years of age. The researcher will give a detail explanation about filling the questionnaire. It has 55 questions including cognitive (22 items), emotional (17 items), social (7 items) and also physical (9 items) function. Items are rated on a five-point Likert scale, 0 = very often, 1 = fairly often, 2 = sometime, 3 = almost never, 5 = never. The composite score is the unweighted average of the four subscales, ranging from 1-100, higher score indicates better quality of life.²⁸

Diary Card

The other important thing to evaluate is subjects' adherence, seizure frequencies, and adverse drug reaction by self-reported diary card which is filled by the parents each day during the intervention phase. Besides, drug consumption compliance is also assessed by counting the tablets or powder packages during routine visits of the study.

Electronic Medical Record

Electronic Medical Record is used to collect secondary data that include demographic data, clinical characteristic, and imaging such as brain-CT or brain-MRI.

Laboratory Examination

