The test is performed in hospitals' laboratory where the study take place and is done twice, at the baseline and post intervention phase. The order of the blood test consists of complete blood test, liver function test including alanine and aspartate transaminase, kidney function test including urea and creatinine, and also blood electrolyte that consist of natrium, kalium and calcium. The laboratory professional takes the blood from vein of the arm. The subjects are seated or lying down, accompanied by the parents, while for the younger children, they seat on his/her parents' lap or position that make them feel comfortable. Older children may be asked to make a fist and then will be tied by a rubber band around his/her arms. After that, the needle is inserted the needle until the blood is drawn. The laboratory worker will take the needle since the amount of blood is enough and puts an adhesive bandage over the site. The next step is analyzes of the sample and the result will be issued for about 1-2 days both printed or provided on the electronic medical record.

Electroencephalography Examination

The EEG examination is operated two times, at the baseline and post intervention phase, with high density machine (Caldwell Easy III) is done twice, pre- and post-intervention. The machine will operate for about 45 minutes including 5 minutes each for eye-open and eye-close in every subjects. Beginning with acquisition, EEG recordings use standard parameter to analyze brain activity at various frequencies to gain good quality and artefact-free result. The printed results of the EEG is available for about 4-7 days after the examination.

Data collection

All relevant data will be recorded, by nominated member(s) of the research team, on a case report form (CRF). Each participant will have a CRF and be assigned a unique identification number.

Baseline data

At entry into the study, the following baseline information will be recorded in the CRF:

- unique patient identification number contact telephone number and/or email address
- date of entry into the study
- eligibility for study entry based on inclusion/exclusion criteria
- age at study entry, in years and months
- gender
- weight and height
- seizure type (eg, generalized tonic clonic, absence, myoclonic and partial)
- the age at diagnosis and duration of epilepsy
- seizure frequency or average number of seizures per month

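### Children removed for worsening have no stated exit assessment, so the EEG, quality-of-life and laboratory comparisons probably leave them out, and no missing-data rule covers the gap

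*Combined protocol and SAP*

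**What the plan says.** **Removal.** Study procedure states that "if the seizures increase more than one and a half time of the previous frequency during the phases, the intervention will be ended immediately". The child goes back to the former combination, and "The subjects are categorized as non-responder, and will be dropped-out". The same section adds: "The children who complete all of the phases are categorized as responder".

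**Timing of the second assessments.** The blood panel "is done twice, at the baseline and post intervention phase". For EEG: "The EEG examination is operated two times, at the baseline and post intervention phase". Study Design describes follow-up of "14 weeks that consist of baseline, intervention, and post-intervention phases", with the post-intervention phase last. The two-weekly visits under Follow-up data collect physical examination, adverse reactions, seizure frequency and type, and complaints. They include no EEG, blood test or QOLCE-55.

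**Quality of life.** The only timing in the readable text is at entry: "Once the children are enrolled, quality of life will be assessed by using validated QOLCE-55 questionnaire". Yet Secondary Objectives sets out "to analyze the differences of improvement of quality of life, EEG feature and time to achieve seizure reduction" between the groups.

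**Analysis.** In Statistical Analysis, EEG falls under item 1, quality of life under item 2 and laboratory findings under item 5. None of these names an analysis set or says what happens to a missing second value. The intention-to-treat and per-protocol pair, and the rule that counts untreated, lost or switched children as failures, stand under item 3, which concerns treatment failure as a yes/no outcome.

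**The concern.** Removal is triggered by a poor outcome, and the second EEG and blood panel sit in a phase that comes after it. If a dropped-out child has no later assessment, the second values are missing because the child did badly. An arm that loses more such children then shows a better average among those left, and part of any true difference between arms disappears.

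The analysis plan does not repair this. A rule that scores a lost child as a failure yields a value for a binary outcome. It yields none for a QOLCE-55 mean or a laboratory result. It could be extended to EEG change, which is a proportion, but the plan does not extend it. A value not collected at exit cannot be recovered later, and three hospitals could each settle the question differently.

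**Working it through.** **1. Inputs from the plan.** Sample size gives response proportions of 0.70 (control) and 0.95 (first-line), 50 children per group, and a 10% drop-out addition (100 to 110). The printed formula with its printed inputs gives 48.91, against the printed 49.56 that is rounded to 50. This relies on the printed Q1 of 0.5, although 1 − 0.95 = 0.05. That is a separate matter, and 50 is used here as the planned group size. The plan gives no figure for how many children will be ended.

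**2. How many could be missing.** Every ended child is a non-responder, so the non-responder count bounds removals for worsening.
- Control: 50 × (1 − 0.70) = 15.
- First-line: 50 × (1 − 0.95) = 2.5.
- Total: 17.5 of 100, against the 10% allowance.

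The share f of non-responders who meet the ending rule is unknown:

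| f | First-line missing | Control missing | Total of 100 |
|---|---|---|---|
| 25% | 0.6 | 3.8 | 4.4 |
| 50% | 1.25 | 7.5 | 8.75 |
| 75% | 1.9 | 11.3 | 13.1 |
| 100% | 2.5 | 15 | 17.5 |

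**3. Effect on QOLCE-55.** Assume a deficit of D = 10 points; the documents give no such figure.
- All non-responders ended: the difference over all randomised children is 10 × (0.30 − 0.05) = 2.5 points. Among those assessed it is 0, so 2.5 points are hidden.
- Half ended, deficit carried by all non-responders: those remaining make up 7.5/42.5 = 0.1765 of assessed control children and 1.25/48.75 = 0.0256 of assessed first-line children. The observed difference is 10 × (0.1765 − 0.0256) = 1.51, so 2.5 − 1.51 = about 1.0 point is hidden.
- Half ended, deficit carried only by ended children: the full difference is 10 × (0.15 − 0.025) = 1.25 and the observed difference is 0, so 1.25 points are hidden.

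These results are proportional to D. At D = 5 they become 1.25, 0.5 and 0.625. They apply only to ages 4–18, the range of the questionnaire, whereas the trial enrols from age 1.

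**4. Effect on EEG.** Assume that 50% of responders and 10% of non-responders improve. Over all randomised children, first-line is 0.95 × 0.5 + 0.05 × 0.1 = 0.48 and control is 0.70 × 0.5 + 0.30 × 0.1 = 0.38, a difference of 10 percentage points. It falls to 0 if all non-responders are ended, and to 0.4 × (0.1765 − 0.0256) = 6 percentage points if half are.

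**The case against.** The strongest reply is that the missed assessments are inferred from silence. No sentence says that a dropped-out child forgoes the second tests. The Electroencephalography section and the abstract also speak of testing before and after intervention, which could mean after that child's own intervention. Ended children stay under treatment until they return to their earlier condition, so contact continues. The timeline and flow-chart figures are not available and might place the final tests. All of this stands as a limit on certainty. It does not remove the problem: dropping out, combined with a phase listed last, makes missing values the natural reading, and the analysis items still have no rule.

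A reader might also infer three stronger things that the documents do not support.
- *Only children who did well are compared.* Outcome evaluation counts as non-responders children whose seizures are unchanged or fall by less than 50%. Nothing says that those who never pass the one-and-a-half-times mark are removed. The statement that all completers are responders conflicts with that definition and does not show who is assessed.
- *Laboratory toxicity is hidden in the children most at risk.* No section links seizure worsening to laboratory abnormality. Laboratory results are summarised descriptively, and adverse reactions are captured by diary and two-weekly visits up to removal. What may be lost is the second blood panel itself.
- *15 versus 2.5 is a forecast.* Those are non-response counts, so they are a ceiling on removals for worsening.

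**Conclusion.** The concern holds in limited form. As written, the plan removes children because of a poor outcome, gives no exit assessment in the readable text, and leaves the EEG, QOLCE-55 and laboratory analyses without an analysis set or missing-data rule. The second QOLCE-55 is not scheduled at all, although improvement is to be compared. The likely result is outcome-dependent missing data, possibly unequal between arms, that favours the arm with more removals. At the planning rates that would be the control arm.

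The size is uncertain. The ceiling is 15 versus 2.5 of 50. With an assumed 10-point deficit, the hidden QOLCE-55 difference is at most 2.5 points, or about 1.0 to 1.25 if half of the non-responders are ended. These figures depend on the planning response rates, the unknown share ended and the assumed deficit. Only secondary and descriptive outcomes are affected, so the change is advisable and does not bear on the primary comparison.

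**What to change.** 1. State that the second EEG, laboratory panel and QOLCE-55 are obtained for every randomised child who can be assessed and consents. If participation ends before the planned final visit, they are done at the visit where it ends. Give the planned time of the second QOLCE-55.
2. Name the analysis set for each of these outcomes and analyse by randomised group.
3. For children still without a second value (death, loss to follow-up, refusal), count EEG as not improved, add a sensitivity analysis for QOLCE-55, and report the number missing by arm for laboratory values.
4. Reconcile Study procedure, which calls every completer a responder, with Outcome evaluation, which requires a fall of at least 50%.

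The cost is small. Two EEGs and two blood panels per child are already planned, so the second is only brought forward for children who stop. The second QOLCE-55 is implied by the objective but has to be scheduled. No treatment rule changes. The drawback is timing: exit values come earlier than completers' values and may be taken while seizures are worse. Report the time of the second assessment by arm, with a sensitivity analysis that addresses it.

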STUDY PROTOCOL

THE EFFICACY AND SAFETY OF FIRST LINE ANTI-EPILEPTIC DRUGS (AEDs) AS SUBSTITUTION THERAPY FOR CHILDREN WITH DRUG RESISTANT EPILEPSY

Protocol Number 22-09-1097

ABSTRACT

Background: Drug resistant epilepsy occurs around 30% of children with epilepsy. It is the failure to get seizure-free after combining two or more anti-epileptic drugs whether first- or second-line ones. Previous studies focus on the efficacy and safety between the two groups whether as add-on or substitution therapy mostly in newly diagnosed epilepsy children. However, the study that investigate first line Anti-epileptic Drugs (AEDs) as substitution therapy compared to second-line ones particularly among drug resistant epilepsy children is still lack. **Design**: It is an open-label, randomized controlled trial, which will be conducted in three referral hospitals in Jakarta, Cipto Mangunkusumo, Harapan Kita, and Fatmawati Hospital, from November 2022 until April 2023. The data will be collected from electronic medical record consisting of demographic, clinical characteristics, and brain CT scan or brain MRI, and diary cards that record daily drug consumption and adverse drug reaction. Self-administered QOLCE-55 questionnaire is used to assess the quality of life of the children. Furthermore, there will be EEG and laboratory examination prior and after intervention. The data will be recorded on Case Report Form that is filled by the researcher. Ethics committee approval is obtained from The Ethics Committee of The Faculty of Medicine, University of Indonesia-Cipto Mangunkusumo Hospital. Research permits would be issued by each institution where the study will take place.

Sample: There will be 100 participants, divided into 2 groups, the intervention and control. Fifty children in the intervention group will be treated with first line AEDs as the substitution therapy, while the other 50 participants in the control group will get second-line AEDs. The sample size is calculated based on the difference proportion of two independent groups.

Duration of the study: The study will take 14 weeks as a whole that consists of 6 phases including baseline, initial, titration, maintenance, tapering-of, stopping and another maintenance phase.

Introduction

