- current anticonvulsant(s) with doses and formulation and its side effect (if presents)
- other medications and its side effect (if presents)

- first recognized seizure date
- prior EEG and laboratory which has been performed at the baseline phase
- physical examination

Follow-up data

Follow-up data will be collected during regularly scheduled clinic visits (per 2 weeks). This information will be obtained from the participants' diary card. Important information to be collected at follow-up will include:

- physical examination
- adverse drug reaction of the substitution therapy that happen
- seizure's frequency
- type of seizure
- complaint

Outcome evaluation

- a. The difference in responders was the difference in the percentage of responders in the group that used first line OAE again as substitution therapy and those that used standard therapy. Responders are subjects who experience a decrease frequency of seizure more than or equal to 50% of the initial seizure. Frequency of seizure is the number of seizures that occur within 1 month. In previous studies, it was said that the frequency of seizures was said to have decreased significantly or was said to respond if the seizures were reduced by 50% or more from the initial seizure. ^{19, 29} Based on this, researchers will categorize the frequency of seizures into:
 - Responder: there is a decrease in the frequency of seizures by 50% or more than before
 - Non-responder: namely the frequency of seizures remains or decreases but not up to 50% of the initial seizure frequency or the frequency is more than before

Furthermore, the proportion in the form of the percentage of respondents in the two groups is calculated and differentiated, therefore it is classified into two groups:

- Different : when a significant difference is shown in difference of proportion test of the 2 unpaired groups.
- Not different: when there is no significant difference is shown in difference of proportion test of the 2 unpaired groups.

- b. Differences in quality of life: quality of life assessment using QOLCE-55 instrument. The average of each function (cognitive, emotional, social and physical functions) and the average of the total functions are assessed. This variable is categorized into:
 - Different, if there is a difference in the average quality of life
 - Not different, if there is no difference in the average quality of life
- c. Differences in electroencephalography appearance

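### The follow-up adverse-reaction item is narrower than the baseline, diary and analysis wording, and no all-cause adverse event collection or table is planned, so some events are liable to be left out of the side-effect tables and the rest depend on open-label attribution

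*Combined protocol and SAP*

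**What the plan says.** Follow-up data lists what is collected at the two-weekly visits. The list opens with "Important information to be collected at follow-up will include", and its adverse-event item reads "adverse drug reaction of the substitution therapy that happen". The other items are physical examination, seizure frequency, seizure type and complaint. On the source, the section says: "This information will be obtained from the participants' diary card".

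Other sections are worded more widely. Baseline data asks for "current anticonvulsant(s) with doses and formulation and its side effect (if presents" and has a separate item for other medications and their side effects. The Abstract describes "diary cards that record daily drug consumption and adverse drug reaction", and Diary Card refers to "adverse drug reaction by self-reported diary card which is filled by the parents each day during the intervention phase". Neither names a drug. Secondary Objectives, Outcome evaluation item d and Statistical Analysis item 5 refer to adverse or side effects of the drugs, to be described by frequency and percentage in each group.

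Study procedure makes withdrawal part of the intervention: after the new drug is titrated and maintained comes "tapering-off and after that stopping the substituted drug, levetiracetam or topiramate", and then maintenance of the new combination. Study Design states that the trial is open label.

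**The concern.** The intervention is a package: start a new drug, withdraw an old one, continue the new drug with those that remain. The Introduction gives the aim as "The new combination is intended to maximize efficacy and minimize toxicity" and names drug interactions among the factors in choosing the new drug. Yet the follow-up item asks only about the new drug. Relief of side effects of the withdrawn drug has no follow-up item either, although those side effects are recorded at baseline.

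The wider wording elsewhere does not fully solve this, because it too asks for reactions to a drug. Someone must suspect a drug before an event counts. The documents do not say who makes that judgement or by what method, and no blinded assessor is described.

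Safety is in the trial's title. Percentages shown by arm will be read as a comparison even though no test is planned, and events not recorded at the time cannot be recovered at analysis.

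**Working it through.** The plan states no figure on this point, so the check is a comparison of the sections, followed by an illustration.

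**Step 1. The sections side by side**

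| Section | What is captured | Limited to one drug? | Must a drug be suspected? |
|---|---|---|---|
| Baseline data | Side effects of current anticonvulsants and of other medication | No | Yes |
| Follow-up data, adverse-reaction item | Reactions to the substitution therapy | Yes | Yes |
| Follow-up data, complaint and physical examination | Not defined further | No | No, but no planned analysis uses them |
| Abstract; Diary Card | Adverse drug reactions, intervention phase only | No | Yes |
| Secondary Objectives; Outcome evaluation d; Statistical Analysis 5 | Adverse or side effects of the drugs | No | Yes |
| Laboratory Examination | Blood count, liver, kidney and electrolytes, twice | No | No |
| Study procedure; Statistical Analysis 3 | Increase in seizures | No | No |

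**Step 2. Route of each kind of event into the safety results**

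- Reaction to the new drug, in any step: fits the follow-up item and the tables.
- Reaction to a retained drug or to the combination: fits the diary and analysis wording but not clearly the follow-up item. The two must be reconciled.
- Non-seizure effect of stopping levetiracetam or topiramate: no dedicated item. It reaches the tables only if someone regards it as a drug reaction.
- Event judged unrelated: no route into the tables. It may be noted as a complaint.
- Laboratory change or seizure worsening: captured in both arms whatever the cause.

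**Step 3. Which arm the item covers**

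The Abstract, Outcome evaluation and Statistical Analysis often use substitution therapy for the first-line arm and contrast it with second-line or standard therapy. Read literally, the follow-up item could apply to one arm only. Statistical Analysis item 5 names both arms, so both are evidently meant, but the item does not say so.

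**Step 4. How much attribution could matter (assumed values, not from the documents)**

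Let t be the true proportion of children with an event, equal in both arms, and a the share attributed to a drug. Then recorded proportion = t × a, and spurious gap = t × (a₁ − a₂).

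- Smallest unequal case: t = 0.20, a = 0.90 and 0.70. Recorded 0.18 and 0.14; gap 0.20 × 0.20 = 0.04.
- Middle case: t = 0.40, a = 0.90 and 0.50. Recorded 0.36 and 0.20, or 18 and 10 of 50; gap 0.40 × 0.40 = 0.16.
- Largest case: t = 0.60, a = 0.90 and 0.50. Recorded 0.54 and 0.30; gap 0.60 × 0.40 = 0.24.
- Equal attribution in both arms: gap 0.

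Children with an unrecorded event, per 50, are 50 × t × (1 − a). In the arm with 90% attribution this is 50 × 0.20 × 0.10 = 1 to 50 × 0.60 × 0.10 = 3. In the other arm it is 50 × 0.20 × 0.30 = 3 to 50 × 0.60 × 0.50 = 15.

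Either arm may be the one with 90%, so the gap may have either sign. The Introduction reports fewer neurotoxic effects with newer drugs, which could make first-line drugs easier to blame. Against that, the first-line drugs are described as being reused, and children with past severe reactions to the drug to be given are excluded. Both could make them harder to blame.

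**The case against.** The strongest reply is that one narrowly worded item is being read without its surroundings. The list is introduced as what collection will include, so it is not exhaustive. Complaints and physical examination are on it and need no drug to be blamed. The diary, named as the source of follow-up data, records adverse drug reactions without restriction. The new drug continues through tapering, stopping and final maintenance, so reactions to it in those steps are covered even by the narrow item. The CRF and diary forms are not in the documents. Laboratory results and seizure worsening do not depend on attribution, and the side-effect summary is descriptive.

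Most of this stands. A reader might infer that events from withdrawal or from the new combination are lost altogether, or that events in half of the intervention steps go unrecorded. The documents do not support either reading, for the reasons just given.

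What remains is narrower. No planned analysis uses complaints or examination findings, so an event noted there does not reach the safety results. The diary is wider than the follow-up item but still asks for reactions to drugs. The absence of a test does not remove bias from percentages displayed by arm.

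**Conclusion.** The point holds as a gap in specification. The follow-up item is narrower than every related section, and all-cause adverse events are neither defined, collected nor tabulated. Non-seizure withdrawal effects and events judged unrelated are liable to be left out of the side-effect tables, and what those tables do show by arm depends on attribution made with the arm known.

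A reader might also infer that the side-effect percentages will be biased against the first-line arm. The documents do not support that: they contain reasons for either direction and give no event rate or attribution rate. The 4 to 24 points above rest wholly on assumed values. They show that unequal attribution could matter in arms of 50, not that it will occur. Laboratory safety and seizure worsening are outside the point.

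This is an inexpensive improvement that should be made. It does not touch the primary outcome.

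**What to change.** In Follow-up data and on the diary card, replace the item with all adverse events, in both arms, whatever the suspected cause. State that it applies equally to both arms, so that the meaning of substitution therapy no longer matters here. Record onset date, study step (initial, titration, maintenance, tapering, stopping, new maintenance) and suspected cause as separate fields. Ask again at follow-up about the side effects recorded at baseline, so that relief as well as new harm can be seen.

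In Statistical Analysis item 5, tabulate all-cause event percentages by arm first and reactions attributed to a drug second. Align Outcome evaluation item d with this.

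Cost: several added CRF and diary fields, one more table, and more events to record, many of them trivial. Collection can use the existing two-weekly visits, and no treatment rule changes.
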